As outlined in section B.6, enrollment will be stopped at an interim analysis for efficacy or futility only if both the primary and secondary efficacy endpoints meet the stopping criteria. Simulations were performed to assess operating characteristics for the primary and secondary efficacy endpoints. We used 8000 trial simulations to estimate the power and 15000 simulations to estimate the type I error. Tables 11 and 12 summarize the assumptions that were made for the primary and secondary efficacy endpoint simulations, and table 13 summarizes the operating characteristics for the efficacy evaluation. The overall power for the efficacy evaluation from table 13 is 94%, with a one-sided type I error rate of 0.026 for 24-hour SBP and 0.028 for Office SBP.

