**Table 13: Operating Characteristics for Primary and Secondary Efficacy Endpoints**

|   |                                       |
|---|---------------------------------------|
| Trial Success Rate (Power)              | 94%                                   |
| Type I Error (one-sided)                | 24-Hr SBP: 0.029
Office SBP: 0.026 |
| First Interim Look N                    | N=210                                 |
| Power at First Interim Look             | 83%                                   |
| Second Interim Look N                   | N=240                                 |
| Power at Second Interim Look            | 89%                                   |
| Maximum Study Size                      | N=300                                 |
| % of Simulations that Stop for Futility | 0.05%                                 |

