# 3. Introduction

This document outlines the detailed statistical methods to be implemented for the data collected within the scope of the Medtronic Vascular SPYRAL PIVOTAL − SPYRAL HTN-OFF MED Study: Global Clinical Study of Renal Denervation with the Symplicity Spyral™ Multi-Electrode Renal Denervation System in Patients with Uncontrolled Hypertension in the Absence of Antihypertensive Medications. The purpose of this study is to obtain an assessment of the efficacy and safety of renal denervation in the absence of antihypertensive medications. Specifically, the SAP has the following purpose: to prospectively outline the types of analyses and presentations of data that will form the basis for conclusions to be reached that will answer the trial objectives outlined in the protocol, and to explain in detail how the data will be handled and analyzed, adhering to commonly accepted standards and practices of biostatistical analysis

in the medical device industry. Results obtained from the analyses outlined in this document will be the basis of the Clinical Study Report for this trial.

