# 8. Determination of Sample Size

This study will be conducted as an adaptive Bayesian trial with an informative prior. A Bayesian power prior approach [3,4] in conjunction with a discount function will be used to incorporate the prior data. The discount function reduces the strength of the prior data if disagreements are observed with the pivotal data.

The prior data consists of the first consecutively randomized 80 patients in the SPYRAL HTN-OFF MED study, the results from these 80 subjects have been analyzed and published [6]. The weight of the prior data will be adjusted using a discount function, which scales from 0 to 1, according to the similarity of the prior and pivotal data. This discount function adjusts the amount of weight the prior receives. This prevents the use of an informative prior where exchangeability issues are present (e.g., the prior and pivotal data are quite different). This discount function approach was proposed by the Medical Device Innovative Consortium (MDIC) working group and is a collaborative effort between FDA and industry through the MDIC [1,2]. If the analyses show a high level of agreement for pivotal data compared to the prior, the prior will be weighted at or near 100%. If the pivotal data perform worse than or much better than the prior, then the prior will receive very little or zero weight. The Bayesian adaptive design is set up to enroll patients until a sufficient sample size is achieved to have high probability of meeting the endpoint.

The sample size of the study will vary from 210 to 300 subjects with 3-month follow-up due to the adaptive nature of the trial. This will require approximately 247 to 353 randomized subjects to account for a 15% attrition at 3-months. Based on this attrition rate, the interim analyses will take place after the 210th and 240th subjects have completed 3-month follow-up, with a maximum study size of 300 subjects if the study does not stop at either interim look. The actual rate of attrition will dictate the available sample size for analyses. At each interim analysis, enrollment may be stopped for efficacy or futility.

Simulations of trial design operating characteristics performed to demonstrate control of type I error & power are presented in section 9.9.6 for the primary and secondary efficacy endpoints.

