## 9.8. Interim Analyses

Interim analyses will be conducted and reviewed by the DSMB, along with an independent organization that will be performing the Bayesian analyses. Medtronic personnel will not have access to any unblinded results prior to the primary endpoint analyses. The interim analyses will take place at N=210 and N=240 subjects with 3-month follow-up, with a maximum study size of N=300 subjects if the study does not stop at either interim look. At each interim analysis, enrollment may be stopped for efficacy or expected futility. Both the primary and secondary effectiveness endpoints will be evaluated during these interim looks and enrollment will only stop at an interim analysis if both endpoints meet the following stopping criteria.

- 1. The first interim analysis takes place when the first 210 subjects have 3-month follow-up data available (requiring approximately 247 randomized subjects to account for attrition). The Bayesian efficacy analysis will be performed and P[suc] will be calculated, where P[suc] is the probability of accepting the alternative efficacy endpoint hypotheses,  $P(\mu < 0 | y, y_0, \widehat{\alpha_0}(y, y_0, \lambda, k))$ , and is defined in detail in section 9.9.3.
  - a. If P[suc] > 0.975 for both the primary and secondary efficacy endpoints, then the study has met the efficacy hypotheses and enrollment will be stopped. Any additional subjects that have been enrolled before the decision is made to stop for efficacy will be pooled with the existing subjects and analyzed as a secondary cohort.
  - b. We calculate the probability of futility based on the maximum study size of 300 subjects which requires us to impute the outcomes for subjects who have not yet been enrolled (see sections 9.8.2 and 9.8.3 below for details). If the posterior probability of futility from this calculation is < 0.05 for both the primary and secondary efficacy endpoints, then the study will have met the futility boundary and enrollment will be stopped. Any additional subjects that have been enrolled before the decision is made to stop for futility will be pooled with the existing subjects and analyzed as a secondary cohort.

  - c. If the stopping rules in a and b above are not met for either the primary or secondary efficacy endpoints, then we continue enrolling subjects to the second interim analysis.

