#### Compare:

We start by stochastically comparing pivotal data vs prior data as follows.

For each treatment group, we separately fit the model to the combined prior and pivotal data:

$$y_i = \tilde{\beta}_0 + \tilde{\beta}_1 I(i \in \text{prior}) + \tilde{\beta}_2 x_i + \varepsilon_i, \quad \varepsilon_i \sim N(0, \tau^2),$$

where  $I(i \in \text{prior}) = 1$  if the subject is from the prior dataset, and 0 otherwise,  $y_i$  is the BP change for the ith observation and  $x_i$  is the mean centered baseline BP for the ith observation. With flat priors on each parameter, we estimate the posterior probability that  $\tilde{\beta}_1 > 0$  by first computing, using Monte Carlo sampling

$$p^* = P[\tilde{\beta}_1 > 0 \mid \mathbf{y}, \mathbf{y}_0].$$

Having calculated this separately for both the RDN  $(p_t^*)$  and control groups  $(p_c^*)$ , they are transformed to  $p_t$  and  $p_c$  using

$$p = \begin{cases} 2p^*, & p^* \le 0.5\\ 2(1-p^*), & p^* > 0.5 \end{cases}$$

Now, under this transformation, if  $p_t$  or  $p_c$  are close to 0, there is a high probability that the pivotal data and prior data come from different populations and discounting should be applied to reduce the influence of the prior. On the other hand, if  $p_t$  or  $p_c$  are close to 1, there is a high probability that the pivotal data and prior data come from similar populations and minimal discounting should be applied.

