# 9.9.6. Simulation of Primary and Secondary Efficacy Endpoint Operating Characteristics

As outlined in section 7.8 enrollment will be stopped at an interim analysis for efficacy or futility only if both the primary and secondary efficacy endpoints meet the stopping criteria. Simulations were performed to assess operating characteristics for the primary and secondary efficacy endpoints. We used 8000 trial simulations to estimate the power and 15000 simulations to estimate the type I error. Tables 3 and 4 summarize the assumptions that were made for the primary and secondary efficacy endpoint simulations, and table 5 summarizes the operating characteristics for the efficacy evaluation. The overall power for the efficacy evaluation from table 5 is 94%, with a one-sided type I error rate of 0.029 for 24-hour SBP and 0.026 for Office SBP.

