**Table 5: Operating Characteristics for Primary and Secondary Efficacy Endpoints** 

Trial Success Rate (Power)	94%
	24-Hr SBP: 0.029
Type I Error (one-sided)	Office SBP: 0.026
First Interim Look N	N=210
Power at First Interim Look	83%
Second Interim Look N	N=240
Power at Second Interim Look	89%
Maximum Study Size	N=300
% of Simulations that Stop for Futility	0.05%

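### The stated type I error (0.029 / 0.026) holds at the pilot arm means; between them it reaches about 0.08, or 0.12 if only 24-h SBP is null, and the protocol text gives other figures

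*SAP*

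**What the plan says.** SAP 9.9.6 summarises the efficacy simulations "with a one-sided type I error rate of 0.029 for 24-hour SBP and 0.026 for Office SBP". SAP Table 5 repeats the pair ("Office SBP: 0.026" for the second endpoint), and protocol Table 13 agrees ("24-Hr SBP: 0.029"). The sentence in protocol H.5.1 that introduces Table 13 reads differently: "with a one-sided type I error rate of 0.026 for 24-hour SBP and 0.028 for Office SBP".

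SAP Tables 3 and 4 list the pilot priors and the pivotal means assumed for power. They give no null means and no correlation between 24-h and office SBP. In SAP 9.9.3 and 9.9.5.1 the null is only that the difference between arms is zero.

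Three design features matter here:

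- The comparison with the pilot is made within each arm: "For each treatment group, we separately fit the model to the combined prior and pivotal data".
- The 0.975 threshold is the same at N=210, 240 and 300.
- At the first two looks, "enrollment will only stop at an interim analysis if both endpoints meet the following stopping criteria". At N=300 each endpoint is judged alone.

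SAP 8 describes the exercise as "Simulations of trial design operating characteristics performed to demonstrate control of type I error & power". SAP 3 adds: "Results obtained from the analyses outlined in this document will be the basis of the Clinical Study Report for this trial".

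**The concern.** A zero difference leaves the common mean change free. With arm-wise discounting, the error rate varies with that mean. If both arms truly change by an amount between the two pilot arm means (24-h: -0.74 and -5.30; office: -2.54 and -9.69), each arm can look compatible with its own pilot arm. The sham prior then pulls the sham arm up while the denervation prior pulls the denervation arm down, which adds a difference that is not there. A single simulated null cannot show control over the whole null hypothesis.

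A reader would take 0.029 as the false-positive rate under the null, in documents that support regulatory submissions. The protocol also gives two different pairs of figures for the same simulation.

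**Working it through.** **Inputs.** SAP Tables 3 and 4:

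| | Pilot RDN mean / SE (n) | Pilot sham mean / SE (n) | Pivotal SD | Planned difference |
|---|---|---|---|---|
| 24-h SBP | -5.30 / 1.65 (35) | -0.74 / 1.62 (36) | 12 | -4.0 |
| Office SBP | -9.69 / 2.20 (37) | -2.54 / 2.09 (41) | 16 | -6.5 |

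The looks fall at 105, 120 and 150 per arm. The success cut-off is 0.975, and early stopping requires both endpoints to pass. The futility stop is omitted, because the plan puts it at 0.05% of simulations. Endpoint correlation is not given, so I assume 0.5 and show 0 to 0.7.

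**Formulas** (SAP 9.9.4.1), for each arm and endpoint:

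1. p = two-sided probability from |pivotal mean - pilot mean| / SE, with variance pooled over pilot and pivotal.
2. Weight a = 1 - exp(-(p/0.5)^3).
3. Posterior precision = n/SD^2 + a/SE0^2; the posterior mean is the precision-weighted average.
4. Success if P(difference < 0) > 0.975.

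**Mechanism, one worked case.** Let both arms truly change by -3, and suppose that by chance 150 per arm give RDN -4 and sham -2.

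- Pivotal data alone: difference -2.0, SE = sqrt(2 x 144/150) = 1.386, z = 1.44, P = 0.926. This fails.
- RDN arm: comparison SE 2.18, z = 1.30/2.18 = 0.596, p = 0.551, a = 0.738. Precisions are 150/144 = 1.042 and 0.738/1.65^2 = 0.271, giving mean -4.27, variance 0.762.
- Sham arm: comparison SE 2.15, z = 1.26/2.15 = 0.585, p = 0.558, a = 0.752. Precisions are 1.042 and 0.752/1.62^2 = 0.286, giving mean -1.73, variance 0.753.
- Combined: difference -2.54, SE = sqrt(0.762 + 0.753) = 1.231, z = 2.06, P = 0.980. This succeeds.

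In the mirror case (RDN -2, sham -4) both weights fall to about 0.017 and the priors drop out. Borrowing therefore reinforces chance differences in one direction only.

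**Reproducing the plan's figures** (300,000 trials per point; Monte Carlo SE 0.0005 at 0.08). Power for 24-h SBP is 93.5%, against 94% stated. With both endpoints null at the pilot sham means, error is 0.029 to 0.030 (24-h) and 0.027 (office), against 0.029 and 0.026. The sponsor's 15,000 runs carry an SE of 0.0014 at 0.029, so these agree.

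**24-h type I error by common 24-h mean, correlation 0.5:**

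| Common mean (mmHg) | Both null, office at -2.54 | Office truly responding by -6.5 |
|---|---|---|
| 0 | 0.025 | 0.040 |
| -0.74 | 0.030 | 0.048 |
| -2 | 0.058 | 0.093 |
| -3 | 0.076 | 0.120 |
| -4 | 0.058 | 0.094 |
| -5.30 | 0.029 | 0.047 |
| -6.5 | 0.026 | not run |

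With both endpoints null the error exceeds 0.05 from about -1.7 to -4.3. At -3 it is 0.072 to 0.078 for correlation 0 to 0.7. With office null at -6 instead of -2.54 it is 0.083 (0.074 to 0.088). With office responding it is 0.118 to 0.121; a shorter run of 40,000 trials gave 0.112 to 0.115.

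Office SBP at a common mean of -6 has error 0.069 to 0.076 with both null, and 0.109 if 24-h SBP responds.

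**Source of the excess, 24-h at -3:**

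| Design | Both null | Office responding |
|---|---|---|
| No borrowing, one look | 0.025 | 0.025 |
| No borrowing, three looks | 0.028 | 0.042 |
| Borrowing, one look (N=300) | 0.070 | 0.070 |
| Borrowing, three looks | 0.076 to 0.083 | 0.120 |

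Borrowing is the main driver. Repeated use of 0.975 matters mostly when the other endpoint responds, because the joint rule then barely restrains early stopping. The false-stop rate at the first look is 0.005 at the pilot sham means, 0.010 to 0.023 with 24-h at -3 and both null, and 0.083 if only 24-h SBP is null.

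**The case against.** - **The null is inferred.** Setting RDN equal to the pivotal control means in Tables 3 and 4 is the natural reading, and what is missing is one sentence and a correlation. The match does not identify the null either: both arms at the pilot RDN means give the same pair. This stands. It does not rescue the claim of control, because both candidates lie at the ends of the range where the error is low.
- **The ratio mixes scenarios.** Against 0.029, the peaks are 0.083/0.029 = 2.9 and 0.120/0.029 = 4.1 times higher. Compared like for like they are 0.076/0.029 = 2.6 with both null, and 0.120/0.048 = 2.5 with office responding. This is a fair caution. A reader has only 0.029 to compare with, so both are worth knowing.
- **The 0.12 case is a corner.** It needs no 24-h effect, the full planned office effect and a common mean near the midpoint. That is so, and the both-null maximum should be reported beside it. A mean of -3 is not remote, though. Pilot mean ± 1.96 SE is -3.9 to +2.4 for sham and -8.5 to -2.1 for RDN, and -3 lies in both. Protocol B.1.1 cites control-arm 24-h falls of 3 and 4.8 mmHg, in different, medicated populations.
- **The SAP shows rates above 0.025 and promises no strict bound.** That is correct, but SAP 8 still says that control was demonstrated.
- **Nothing changes for the trial.** Enrollment stopped at the first look with both posterior probabilities above 0.999. This is conceded: the point concerns how the design is described.

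**Conclusion.** The concern holds. The stated 0.029 / 0.026 is reproducible, but it describes the error at the pilot arm means and not the maximum under the null. Over the common mean change, the maximum with both endpoints null is about 0.08 for 24-h SBP and 0.075 for office SBP; when only that endpoint is null it is about 0.12 and 0.11. At or outside the pilot arm means, the both-null error is about 0.03 or lower.

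These figures rest on the Table 3 and 4 SDs, an assumed correlation of 0.5 and a pooled comparison variance. With an unpooled variance the both-null peaks are 0.073 and 0.066, and the 24-h peak with office responding is 0.108. A 24-h SD of 10 or 14 in place of 12 moves that last peak to 0.09 or 0.15. The conclusion does not depend on these choices.

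The protocol H.5.1 sentence is a plain inconsistency. It is not a simple swap of the two endpoints, since 0.028 appears in neither table. The reported efficacy result is not overturned. This should be fixed because the documents feed the study report.

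**What to change.** 1. In SAP 9.9.6 / Table 5 and protocol H.5.1 / Table 13, state the null means and endpoint correlation that were simulated. From the sponsor's own code, add two figures per endpoint: the maximum type I error over the common mean with both endpoints null, and the maximum when only that endpoint is null.
2. In SAP 8, say that the simulations describe type I error and power, including that maximum, instead of saying that they demonstrate control.
3. Correct the protocol H.5.1 sentence to 0.029 (24-h) and 0.026 (office).
4. Optional: report the posterior with zero pilot weight beside the borrowed one, logged in SAP 9.13 as a sensitivity analysis added after the interim result. The alternative analysis reported in protocol B.1.2 uses the overall population, so it does not isolate the pivotal data.

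The cost is a grid re-run of existing code and edits to two SAP sections and one protocol section (SAP 9.13 as well if item 4 is taken up). The stated error rate becomes less favourable. Conduct, sample size and the decision rule are unchanged.

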**Table 3: Simulation Assumptions for Primary Efficacy Endpoint** 

Enrollment Rate	10 Subjects / Month
Prior Baseline Adjusted RDN Group Mean/SE	-5.30 / 1.65 mmHg
Prior RDN Group N	35
Prior Baseline Adjusted Control Group Mean/SE	-0.74 / 1.62 mmHg
Prior Control Group N	36
Maximum Prior Patients	35 RDN + 36 Control = 71
Pivotal Study Expected Treatment Difference	-4.0 mmHg
Pivotal Study RDN Group Mean/SD	-4.74 / 12 mmHg
Pivotal Study Control Group Mean/SD	-0.74 / 12 mmHg

Weibull Discount Function Parameters	Shape: $k = 3$ , Scale: $\lambda = 0.5$
WCDUII DISCOULL LUICUOLLI UI ALAITICUCIS	$  J   apc. \kappa - J, J   apc. \kappa - 0.5$

**Table 4: Simulation Assumptions for Secondary Efficacy Endpoint** 

Enrollment Rate	10 Subjects / Month
Prior Baseline Adjusted RDN Group Mean/SE	-9.69 / 2.20 mmHg
Prior RDN Group N	37
Prior Baseline Adjusted Control Group Mean/SE	-2.54 / 2.09 mmHg
Prior Control Group N	41
Maximum Prior Patients	37 + 41 = 78
Pivotal Study Expected Treatment Difference	-6.5 mmHg
Pivotal Study RDN Group Mean/SD	-9.04 / 16 mmHg
Pivotal Study Control Group Mean/SD	-2.54 / 16 mmHg
Weibull Discount Function Parameters	Shape: $k = 3$ , Scale: $\lambda = 0.5$

**Table 5: Operating Characteristics for Primary and Secondary Efficacy Endpoints** 

Trial Success Rate (Power)	94%
	24-Hr SBP: 0.029
Type I Error (one-sided)	Office SBP: 0.026
First Interim Look N	N=210
Power at First Interim Look	83%
Second Interim Look N	N=240
Power at Second Interim Look	89%
Maximum Study Size	N=300
% of Simulations that Stop for Futility	0.05%

#### 9.9.7. Secondary Analysis of Primary and Secondary Efficacy Endpoints

According to section 7.8, the first and second interim analyses takes place when the first 210 and 240 subjects have 3-month follow-up data available respectively. At each interim analysis, the Bayesian efficacy analysis will be performed, and a decision can be made to stop the study for futility or efficacy.

If the study stops for efficacy or futility at either the first or second interim analysis, then any additional subjects that have been enrolled before the decision to stop has been made will not be part of the primary endpoint analysis, but instead will be pooled with the existing subjects and analyzed as a secondary cohort. The same analysis outlined in section 9.9.4 and 9.9.5 will be used on this pooled cohort.

#### 9.9.8. Other Secondary Efficacy Endpoints

The following additional secondary efficacy endpoints will be assessed:

- Change in systolic blood pressure (SBP) from baseline (Screening Visit 2) as measured by 24-hour Ambulatory Blood Pressure Monitoring (ABPM) at 3, 6, 12, 24 and 36 months post-procedure.
- Change in office systolic blood pressure from baseline (Screening Visit 2) at 1, 3, 6, 12, 24 and 36 months post-procedure.
- Incidence of achieving target office systolic blood pressure (SBP <140 mmHg) at 1, 3, 6, 12, 24 and 36 months post-procedure.
- Change in office diastolic blood pressure from baseline (Screening Visit 2) at 1, 3, 6, 12, 24 and 36 months post-procedure.
- Change in diastolic blood pressure from baseline (Screening Visit 2) as measured by 24-hour Ambulatory Blood Pressure Monitoring (ABPM) at 3, 6, 12, 24 and 36 months post-procedure.

RDN vs. control groups will be compared out to 6-months post randomization, prior to the crossover procedure. Statistical comparisons will be performed using the independent samples t-test for continuous endpoints and Fisher's exact test for categorical endpoints. In addition, two-sided 95% confidence intervals of the difference between RDN and control groups will be presented. Changes in blood pressure measurements from baseline to follow-up within each treatment group will be assessed using paired t-tests. Two-sided 95% confidence intervals of the mean change from baseline will be presented for each treatment group. Analysis of Covariance (ANCOVA) models, adjusting the treatment effect for the baseline BP measurements will also be applied to all continuous secondary endpoints.

RDN vs. Crossover vs. Non-Crossover groups will be compared out to 36 months post-procedure for the RDN and Non-Crossover groups and out to 24 months for the Crossover group using chi-square tests for categorical data and ANOVA for continuous data.

Changes in blood pressure measurements from baseline to follow-up within each group will be assessed using paired *t*-tests. Two-sided 95% confidence intervals of the mean change from baseline will also be presented for each group.

The secondary efficacy analyses will be presented for all the study populations defined in section 9.1.3.

